12.4.3. Safety

Adverse Events
AEs of Special Interest (AESI)

• Clostridium difficile events• Cardiovascular events• Gastrointestinal events• Acetylcholinesterase inhibition events

List of Cardiovascular AESIs Preferred Terms	
Pulmonary oil microembolism	Atrioventricular node dispersion
Peripheral revascularization	Cardiac arrest
Supraventricular extrasystoles	Holiday heart syndrome
Rebound tachycardia	Anomalous atrioventricular excitation
Cardio-respiratory arrest neonatal	Bundle branch block
Atrial conduction time prolongation	Adams-Stokes syndrome
Cardiac death	Atrioventricular dissociation
Paroxysmal arrhythmia	Atrial flutter
Cardiac flutter	Prosthetic cardiac valve thrombosis
Neonatal sinus bradycardia	Heart valve incompetence
Neonatal bradyarrhythmia	Cardiac valve disease
Sinus bradycardia	Metastatic pulmonary embolism
Bradycardia foetal	Renal revascularisation surgery
Junctional ectopic tachycardia	Angina unstable
Ventricular fibrillation	Ventricular extrasystoles
Accessory cardiac pathway	Lenegre's disease
Sinoatrial block	Atrioventricular block
Pulseless electrical activity	Nodal arrhythmia
Ventricular parasystole	Rhythm idioventricular
Paroxysmal atrioventricular block	Nonreassuring foetal heart rate pattern
Ogden syndrome	Ventricular asystole
Nodal rhythm	Defect conduction intraventricular
Bundle branch block left	Atrial fibrillation
Heart valve stenosis	Tachycardia foetal
Acute myocardial infarction	Atrioventricular block first degree
ECG signs of myocardial infarction	Foetal arrhythmia
Embolism arterial	Neonatal tachycardia
Pulmonary embolism	Carcinoid heart disease
Central bradycardia	Cardiac valve replacement complication
Sinus arrest	Degenerative multivalvular disease
Cardiac fibrillation	Cardiac valve sclerosis
Trifascicular block	Cardiac valve abscess
Ventricular tachycardia	Newborn persistent pulmonary hypertension
Accelerated idioventricular rhythm	Deep vein thrombosis postoperative
Bundle branch block bilateral	Carotid revascularization
Bundle branch block right	Transmyocardial revascularization
Bezold-Jarisch reflex	Ventricular tachyarrhythmia
Chronotropic incompetence	Tachycardia
Arrhythmia neonatal	Torsade de pointes
Inherited cardiac conduction disorder	Lown-Ganong-Levine syndrome
Baseline foetal heart rate variability disorder	Conduction disorder
Ventricular flutter	Congenital supraventricular tachycardia
Lambli's excrescences	Pacemaker generated arrhythmia
Periprocedural myocardial infarction	Wolff-Parkinson-White syndrome
Congenital pulmonary hypertension	Long QT syndrome
Portopulmonary hypertension	Parasystole
Deep vein thrombosis	Cardiac arrest neonatal
Revascularisation procedure	Neonatal sinus tachycardia
Cardiac failure congestive	Foetal tachyarrhythmia
Atrioventricular node dysfunction	Cerebrovascular disorder
Ventricular pre-excitation	Pulmonary arterial hypertension
Supraventricular tachyarrhythmia	Post procedural pulmonary embolism
Arrhythmia	Pulmonary microemboli

Cerebral revascularization	Supraventricular tachycardia
Timothy syndrome	Sinusoidal foetal heart rate pattern
Heart alternation	Bradyarrhythmia
Reperfusion arrhythmia	Tachycardia paroxysmal
Foetal heart rate disorder	Sinus tachycardia
Atrial parasystole	Wandering pacemaker
Atrial tachycardia	Withdrawal arrhythmia
Bifascicular block	Foetal heart rate acceleration abnormality
Atrioventricular block complete	Pacemaker syndrome
Sudden cardiac death	Structural valve deterioration
Sinus node dysfunction	Cardiac valve thickening
Sudden death	Post procedural myocardial infarction
Cardio-respiratory arrest	Pulmonary hypertension
Arrhythmia supraventricular	Obstetrical pulmonary embolism
Neonatal tachyarrhythmia	Heart block congenital
Bradycardia	Atrioventricular block second degree
Congenital heart valve incompetence	Extrasystoles
Cardiac valve rupture	Brugada syndrome
Heart valve calcification	Wolff-Parkinson-White syndrome congenital
Cardiac valve discolouration	BRASH syndrome
Cardiac valve vegetation	Ventricular arrhythmia
Congenital heart valve disorder	Foetal heart rate deceleration abnormality
Myocardial infarction	Long QT syndrome congenital
Silent myocardial infarction	Agonal rhythm
Septic pulmonary embolism	Frederick's syndrome
Coronary revascularization	Bradycardia neonatal
Atrioventricular conduction time shortened	Shone complex
Sinus arrhythmia	Transient ischaemic attack
Tachyarrhythmia	Cerebrovascular accident
Postural orthostatic tachycardia syndrome	

List of Acetylcholinesterase Inhibition AESIs Preferred Terms	
Abdominal discomfort	Generalised non-convulsive epilepsy
Abdominal pain	Generalised tonic-clonic seizure
Abdominal pain lower	Heart rate decreased
Abdominal pain upper	Hyperhidrosis
Abdominal symptom	Hyperkinesia
Abdominal tenderness	Hypocalcaemic seizure
Asthma	Hypoglycaemic seizure
Atonic seizures	Hyponatraemic seizure
Atypical benign partial epilepsy	Idiopathic generalised epilepsy
Autonomic seizure	Idiopathic partial epilepsy
Bradycardia	Irregular breathing
Bradycardia	Lacrimation increased
Bronchial hyperreactivity	Lafora's myoclonic epilepsy
Bronchospasm	Lennox-Gastaut syndrome
Clonic convulsion	Myoclonic epilepsy
Cold sweat	Nausea
Convulsions local	Night sweats
Convulsive threshold lowered	Partial seizures
Defaecation urgency	Partial seizures with secondary generalisation
Diarrhoea	Petit mal epilepsy
Drizzling	Psychomotor hyperactivity
Dyspnoea	Retching
Dyspnoea at rest	Salivary hypersecretion
Dyspnoea exertional	Seizure
Epigastric discomfort	Seizure cluster
Epilepsy	Simple partial seizures
Epilepsy with myoclonic-atonic seizures	Status asthmaticus
Faeces soft	Status epilepticus
Febrile convulsion	Sweat gland disorder
Febrile infection-related epilepsy syndrome	Syncope
Flatulence	
Focal dyscognitive seizures	Tonic clonic movements
Frequent bowel movements	Tonic convulsion
Frontal lobe epilepsy	Unilateral bronchospasm
Gastrointestinal disorder	Vomiting
Gastrointestinal pain	Vomiting projectile
Gastrointestinal tract irritation	Wheezing
Adverse Events with Missing Relationship or Missing Serious Indicator	

 • If the relationship to study treatment is missing for a treatment-emergent AE (TEAE), then the TEAE will be considered related to the study treatment. • If the serious indicator "Was event serious?" is missing, the AE will be considered as SAE. • Adverse events with missing relationship or missing serious indicator will be presented as it is in listings but will be treated as related AEs or SAEs in summary tables. 	

Laboratory Parameters

If a laboratory value which is expected to have a numeric value for summary purposes, has a non-detectable level reported in the data base, where the numeric value is missing, but typically a character value starting with '<=', '>=', '>', '<' (or indicated as less than x or greater than x in the comment field) or is present, the number of significant digits (i.e. decimal places) in the observed values will be used to determine how much to add or subtract in order to impute the corresponding numeric value.

Laboratory Parameters

1. Example 1: 2 significant digits = ' $\leq x$ ' becomes $x - 0.01$ (Note: also applies to ' $< x$ ')
2. Example 2: 1 significant digit = ' $\geq x$ ' becomes $x + 0.1$ (Note: also applies to ' $> x$ ')
3. Example 3: 0 significant digits = ' $\leq x$ ' becomes $x - 1$ (Note: also applies to ' $> x$ ')

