- Updated disk diffusion summary statistics to include median and standard deviation but not include the mode and add that results will not be displayed if <10 isolates (Section 7.3.1.2).
- Added that the relatedness of pre- and post-baseline isolates (e.g., as it relates to 4-fold increases and/or microbiological failures) will be described in a stand-alone report, if needed (Section 7.3.1.3).
- Added that analyses of reduction in susceptibility may be repeated for study treatments by phenotypic and genotypic subgroups (Section 7.3.1.3).
- Clarified that the relatedness of pre- and post-baseline isolates (e.g., as it relates to 4-fold increases and/or microbiological failures) will be described in a stand-alone report, if needed (Section 7.3.1.3).
- Updated NAAT FU analyses (Pharyngeal NG and Urogenital Mgen) of microbiological response to be unadjusted since it is anticipated that there will be insufficient observations to adequately perform an adjusted analysis (Section 7.3.1.5).
- Added clarification that both CLSI and EUCAST versions of the Micro Review Aid will be created (Section 7.3.1.6).
- Added non-serious drug-related AEs to AE types to be summarised (Section 8.1)
- Added Cockcroft-Gault formula for determination of renal impairment by baseline CrCL (Section 8.3).
- Clarified that Adverse Reactions will be reported in the regulatory submission but are not required as part of the CSR (Section 8.5).
- Updated Benefit-Risk analysis to additionally include incidence of any AE (Section 10).
- Updated references (Section 11).
- Added data-handling instructions relating to extra NAAT specimens i.e., where both urine and swab specimen are taken for the central laboratory urogenital NAAT at the same visit/timepoint (Section 12.4.2).
- Added further clarification on the Keepers file process (Section 12.4.2).
- Added clarification on the determination and handling of Out-of-Stability samples (Section 12.4.2).
- Updated instructions on handling laboratory values with non-detectable levels reported in the data base (Section 12.4.3).
- Updated output numbering, titles and programming notes in list of data displays as required and included additional summaries added in this RAP update (Appendix 9, Section 12.9).

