 - When serial two-fold dilution MICs are being prepared and tested, the actual dilution scheme is, e.g.: 16, 8, 4, 2, 1, 0.5, 0.25, 0.125, 0.0625, 0.03125, 0.015625, 0.0078125 ug/ml, etc.
 - For convenience only, it was decided to use the following values for reporting purpose (reporting format): 16, 8, 4, 2, 1, 0.5, 0.25, 0.12, 0.06, 0.03, 0.015, 0.008, 0.004, 0.002 ug/mL, etc. The values that appear in the tables are equivalent to the actual values tested, e.g., 0.12 ug/mL = 0.125 ug/mL; 0.015 ug/mL = 0.015625 ug/mL.
 - Any values contain '<', '<=', '>=', '>' will be counted in its separate categories. However, when calculating the minimum, maximum, MIC₅₀, MIC₉₀, a small amount will be added or subtracted in order to impute the corresponding numeric value for calculation. For example,
 - '<0.06' will be imputed as 0.06-0.001;
 - '>256' will be imputed as 256+0.001.
 - '>=32' will be imputed as 32.
 - But for reporting, they will still be presented in original format if they happen to be those summary statistics.
 - Disk diffusion will be conducted on all NG isolates as follows:

Compound	Organisms
Gepotidacin ^a	All NG isolates
Ceftriaxone	All NG isolates
Azithromycin	All NG isolates
^a Two manufacturers (Becton Dickinson and MAST)	

- Disk diffusion results will be reported according to approved microbiology standards (e.g. CLSI or EUCAST, note that there are currently no EUCAST disk diffusion interpretive criteria for *N. gonorrhoeae*). The zone size will be recorded and reported in millimeters along with the interpretation code (S=susceptible, I=intermediate, R=resistant, NS=nonsusceptible) for disk diffusion results. Where no interpretation is available, only zone diameters will be recorded.
- Urogenital, pharyngeal, and rectal specimens for NAAT will be collected from all participants at designated visits (refer to Table 6) and processed as outlined below at the central laboratory:
 - Detection of NG and CT (Positive or Negative)
 - Detection of Mgen and five macrolide resistance markers (Detected or Not Detected)
 - Detection of ciprofloxacin resistance markers in NG (Detected or Not Detected)
 - Detection of gepotidacin resistance markers in NG (Detected or Not Detected)
- Testing for Beta-lactamase production will be performed on all NG isolates. Results will be reported as β-lactamase positive or β-lactamase negative.

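### Read literally, the SAP's integer example for censored laboratory values turns a `>x` result into x − 1, below the limit it exceeds

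*SAP*

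**What the plan says.** SAP 12.4.3, under Laboratory Parameters, deals with laboratory values that should be numeric but arrive with a qualifier. The qualifiers covered are `<=`, `>=`, `>` and `<`, and also results "or indicated as less than x or greater than x in the comment field". The governing sentence fixes the size of the step: the number of decimal places in the observed values "will be used to determine how much to add or subtract in order to impute the corresponding numeric value". It does not say which qualifiers are added to and which are subtracted from. Only the three examples show direction:

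- "Example 1: 2 significant digits = ' $\leq x$ ' becomes $x - 0.01$ (Note: also applies to ' $< x"
- "Example 2: 1 significant digit = ' $\geq x$ ' becomes $x + 0.1$ (Note: also applies to ' $> x"
- "Example 3: 0 significant digits = ' $\leq x$ ' becomes $x - 1$ (Note: also applies to ' $> x"

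Each quote stops at the symbol named in the note. In Examples 1 and 2 the note extends the rule to the matching strict inequality (`<` with `<=`, `>` with `>=`). In Example 3 it extends a subtraction to `>`.

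The SAP has a separate rule for MIC values in 12.4.2, where ">256' will be imputed as 256+0.001".

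The laboratory rule is operative text. The revision table in SAP section 1 records for Amendment 2: "Updated instructions on handling laboratory values with non-detectable levels reported in the data base (Section 12.4.3".

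**The concern.** A result of `>x` says that the true value lies above x. An imputed value of x − 1 lies on the wrong side of the limit, so the stored number contradicts the report it stands for. The same qualifier moves up when the result has one decimal and down when it has none, and the SAP gives no reason for the difference.

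Results above a reporting limit are high values, and the literal rule makes them look lower. The imputed numbers would enter the change-from-baseline summaries for chemistry and hematology (Tables 3.201 and 3.203). If grading is run on the imputed values, they would also enter the maximum-grade tables (3.202 and 3.204). A derivation rule in a SAP is meant to be programmed as written. Here a programmer must either follow the line or depart from it without authority.

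**Working it through.** **Inputs.** The step rule and the three examples come from SAP 12.4.3, the MIC comparison from SAP 12.4.2, and the grade limits from SAP 12.7.1.1.

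**Step size.** With d decimal places the step is 10^(−d): 0.01 for d = 2, 0.1 for d = 1 and 1 for d = 0. All three examples reproduce these sizes, so the amount is not in question, only the direction.

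**Direction.** Each stated pair of qualifier and precision is applied literally to an illustrative limit and checked against its own inequality.

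| Example | d | Reported | Stored | Agrees with the report? |
|---|---|---|---|---|
| 1 | 2 | `<=5.00` | 4.99 | yes |
| 1 | 2 | `<5.00` | 4.99 | yes |
| 2 | 1 | `>=5.0` | 5.1 | yes |
| 2 | 1 | `>5.0` | 5.1 | yes |
| 3 | 0 | `<=100` | 99 | yes |
| 3 | 0 | `>100` | 99 | **no** |

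Five of the six pairs are coherent; only the note in Example 3 fails. The result does not depend on the limit chosen. For `>5`, `>60`, `>100` and `>300` the literal note gives 4, 59, 99 and 299, while the direction of Example 2 with an integer step gives 6, 61, 101 and 301. The two conventions always differ by (x + 1) − (x − 1) = 2.

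**Comparison within the SAP.** The MIC rule sends `>256` to 256 + 0.001 = 256.001, which is upward. It leaves `>=32` at 32, so it bears on the direction for `>` and not on the step size or on `>=`.

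**What the examples leave open.** As written, no example with zero decimals covers `<x` or `>=x`. If the note is corrected to `<x`, both lower-limit qualifiers are covered, but `>x` and `>=x` with zero decimals then rest only on analogy with Example 2.

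**When a grade could change.** x − 1 and x + 1 fall in different grades only if a grade boundary lies between them. The numeric hypernatremia limits are Grade 3 for 158 to 165 mEq/L and Grade 4 above 165. Taking assumed integer reporting limits x:

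| x | Literal x − 1 | Upward x + 1 | Grades |
|---|---|---|---|
| 164 | 163 | 165 | 3 and 3 |
| 165 | 164 | 166 | **3 and 4** |
| 166 | 165 | 167 | **3 and 4** |
| 167 | 166 | 168 | 4 and 4 |

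Only a limit on the cut-off or next to it matters. Away from a cut-off nothing changes: glucose `>300` mg/dL becomes 299 or 301, and both are Grade 3 (251 to 500). In the sodium case the participant would still appear in the listing of Grade 3 or higher chemistry toxicities (Listing 901); only the grade would differ.

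**The case against.** The strongest reply is that this is one wrong character and not a chosen method. The three lines are labelled as examples, Example 2 states the direction for `>` plainly, Example 1 pairs `<=` with `<`, and the MIC rule agrees. A competent programmer would notice the conflict. The text was also read from PDF by a program, so a misread symbol cannot be fully excluded.

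Much of this stands. A slip for `<x` is the likeliest explanation, and the symbol should be checked against the source file. It does not clear the text, however. The neighbouring symbols are coherent, the governing sentence gives no direction that would override the note, and nobody should have to guess which line of a derivation rule to ignore.

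Three stronger readings are tempting, and the documents do not support them.

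- **Hematuria grading.** A reader might infer that a urine red-cell count of `>10` per field, stored as 9, drops from Grade 2 to Grade 1. SAP 8.3 plans only categorical summaries of dipstick results and a listing of urinalysis data. The graded tables, 3.202 and 3.204, cover chemistry and hematology, and the urinalysis table, 3.205, is for dipstick results. The hematuria criteria also combine count with appearance, so the count alone does not settle the grade.
- **An error of 2 units per value.** The true value behind `>x` is unknown, and x + 1 is itself a convention. Two units is the gap between two conventions, not a measured error.
- **An error introduced by Amendment 2.** The revision table says that the instructions were updated. It does not show what changed.

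**Conclusion.** Wrong as written, and minor. Read literally, the Example 3 note gives an integer `>x` result a value that the report excludes, against Example 2 for the same qualifier and against the SAP's own MIC rule.

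The effect is confined to numeric chemistry and hematology safety summaries of results reported as `>x` with no decimals. How many there will be is unknown, because the documents give no reporting limits; the number is probably very small and may be zero. Any change of grade is hypothetical and rests on two assumptions: that a reporting limit lies on or next to a cut-off, and that grading uses the imputed number, which 12.4.3 does not say. Where a grade did change, it would understate a high value. The primary and secondary efficacy endpoints do not use this rule, and MIC results have their own.

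**What to change.** In SAP 12.4.3, change the note in Example 3 so that it applies to `< x`, and add one line stating that with 0 decimals `>= x` and `> x` become x + 1. Better still, state the direction once in the governing sentence (`<` and `<=` move down, `>` and `>=` move up, by one unit of the last decimal place), so that it does not depend on the examples. Confirm the symbol against the source file, and confirm that the derivation program moves `>` results up at every precision.

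The cost is one or two lines of SAP text and a short program check. No new data or tables are needed.

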12.5. Appendix 5: Reporting Standards for Missing Data

12.5.1. Premature Withdrawals

Element	Reporting Detail
General	
 Participant study treatment completion is defined as if the participant has taken all doses of the study treatment and completed the TOC Visit. Participants who discontinue study treatment will not be considered withdrawn from the study and should attend the TOC and Follow-up Visits as applicable. Participant study completion (i.e., as specified in the protocol) is defined as if the participant has completed all study visits including the Follow-up Visit. Withdrawn participants will not be replaced in the study. All available data from participants who were withdrawn from the study will be listed and data will be included in summary tables and figures as described in Section 5.6 on Analysis Visits.

12.5.2. Handling of Missing Data

Element	Reporting Detail
General	
 Missing data occurs when any requested data is not provided, leading to blank fields on the collection instrument: 
 These data will be indicated by the use of a “blank” in participant listing displays. Unless all data for a specific visit are missing in which case the data is excluded from the table. Answers such as “Not applicable” and “Not evaluable” are not considered to be missing data and should be displayed as such.
Primary and Secondary Efficacy	
 Participants who do not return for the TOC visit will be treated as failures. Participants who withdraw from the study prior to TOC will be considered not achieving success for the microbiological response. Microbiological outcome for these participants will be imputed as failures. Any participant in whom a determination of the baseline pathogen microbiological outcome cannot be made at TOC (e.g., no bacteriological sample taken for culture, sample lost, sample plated out of stability, etc.) will be considered as failures.
Outliers	
 Any participants excluded from the summaries and/or statistical analyses will be documented along with the reason for exclusion in the clinical study report.

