- m. During the Baseline Visit, participants randomly assigned to ceftriaxone plus azithromycin will receive a single IM dose of ceftriaxone (500 mg) plus a single oral dose of azithromycin (1 g). See Section 7.1. Azithromycin should be taken after food consumption and with water.
- n. Record serious adverse events from the time of consent/assent in order to fulfill international regulatory requirements.
- o. Record adverse events from the time of the first dose of study treatment.
- p. Confirm return day/time for the TOC and Follow-up Visits.
- q. Previsit reminder: Study site staff will contact the participant 24 ± 4 hours before the respectively scheduled Baseline (if applicable), TOC, or Follow-up Visit.
- r. Participants who tested positive for CT and/or Mgen per NAAT results at the Baseline Visit should be treated per local standard of care at or after the TOC Visit or at the Follow-up Visit (if treatment has not already been initiated), as required, after all study procedures at the visit have been completed.
- s. Collect sample only if the participant has a signed consent/assent specific for this purpose. The Baseline Visit is the recommended time to collect the sample; however, it can be collected at any time during the study.

Table 2 Collection of Bacteriology and NAAT Microbiological Specimens

Visit	Baseline	TOC ^a	Follow-up	Early Withdrawal
Study Day	1	4 to 8	14 to 21	NA
Collection Type Anatomical Site ^b – Organism	Pre-dose	NA	NA	NA
Bacteriology sample collection ^b				
Urogenital – NG ^c	X	X		X
Pharyngeal – NG ^d	X	X	X ^e	X
Rectal – NG ^d	X	X		X
NAAT assay sample collection ^f				
Urogenital – NG and CT ^g	X	X ^h		X
Urogenital – Mgen ^g	X		X ⁱ	X
Pharyngeal – NG and CT ^j	X	X	X ^k	X
Rectal – NG and CT ^j	X	X		X

CT=*Chlamydia trachomatis*; Mgen=*Mycoplasma genitalium*; NA=not applicable; NAAT=nucleic acid amplification test; NG=*Neisseria gonorrhoeae*; TOC=Test-of-Cure.

- Any participant that withdraws before TOC should have all bacteriology and NAAT assay collections performed as indicated at the TOC Visit.
- Multiple swab specimens and types may need to be obtained from each anatomical site; refer to the laboratory manual.

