8.2. Withdrawal From the Study

- A participant may withdraw from the study at any time at his or her own request or may be withdrawn at any time at the discretion of the investigator for safety, behavioral, compliance, or administrative reasons.
- Reasons for study withdrawal include:
 - Participant lost to follow-up
 - Participant withdrew consent
 - Termination of the study by GSK
 - Investigator discretion
- If the participant withdraws consent for disclosure of future information, the sponsor may retain and continue to use any data collected before such a withdrawal of consent.
- If a participant withdraws from the study, he or she may request destruction of any samples taken and not tested, and the investigator must document this in the site study records.
- Participants who withdraw from the study should be encouraged to return for the TOC and/or Follow-up Visits. Refer to Table 1 for data to be collected at these visits.
- The reason for participant withdrawal will be recorded in the eCRF. Participants who were randomly assigned to gepotidacin should return all unused study treatment.

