5.6. Analysis Visits

Due to participants potentially returning outside the protocol scheduled visit window, analysis visit windows will be defined for by-visit summaries and analysis purposes as illustrated in the table below. Data not reported by-visit, including adverse events and concomitant medications, will not employ analysis visits. Analysis visit labels will be assigned to each post-baseline record (including records from unscheduled and early termination visits) based on the corresponding study day (relative to first study treatment or randomization if not treated). For post-baseline records collected outside the analysis visit window, a blank analysis visit label will be assigned. For example, a record collected at study Day 11 will not be utilized in any analyses conducted at the TOC or FU scheduled visit. Descriptive summaries that are shown for “any assessment post baseline” e.g., maximum/minimum/ worst case post baseline, will use all assessments irrespective of whether they fall in an analysis visit window. There are no scheduled FU assessments for Urogenital (except Mgen participants) or rectal body site, but it is possible that any unscheduled assessment or a late TOC fall into this FU window and in that case FU visit will not be presented in summaries but in listings it will be included.

Scheduled Post-baseline Visit	Protocol Window	Target Day	Analysis Visit Window (Days)
Test-of-Cure	4 to 8	6	4 to 10
Follow-up	14 to 21	18	13 to 24

If multiple records exist within the same analysis visit window, then the record occurring closest to the target day will be utilized in all analyses and analysis population determinations. If multiple records are equally close to the target day, then the later record will be utilized. If multiple records occur on the same day and time is not collected, then the record with the larger Study Data Tabulation Model (SDTM) record sequence number will be utilized in all analyses. All protocol scheduled assessments (including unscheduled and early termination visits) will be presented in subject listings. Both the nominal and analysis visit will be presented in listings.

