7.2.6. Statistical Analyses / Methods

7.2.6.1. Statistical Methodology Specification

There will be no multiplicity adjustment for the testing of the secondary endpoints. No formal hypothesis testing will be performed; 95% CIs may be included but only for descriptive purposes. Microbiological response and microbiological outcome for NG from pharyngeal or rectal body sites will be summarized using the Micro-ITT Rectal, Micro-ITT Pharyngeal, ME Rectal and ME Pharyngeal populations for respective body sites. The number and percentage of participants with culture-confirmed bacterial eradication of NG from the rectal body site will be summarized at the TOC visit by treatment group. The corresponding 95% Exact (Clopper-Pearson) CIs will be summarized for each treatment group. The same analysis will also be presented for the pharyngeal body site. The unadjusted difference in microbiological success rate for the two treatments (gepotidacin – ceftriaxone plus azithromycin) will be calculated and summarized along with its 2-sided 95% CI using MN method (adjustment for strata will not be performed).

Participants who do not return for the TOC visit (or have missing data at TOC for any other reason) will be treated as failures. Participants who withdraw from the study prior to TOC will be considered not achieving success for the microbiological response and will be imputed as failures.

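### The SAP gives two opposite scores to a participant who withdraws before TOC but has a negative, evaluable culture inside the TOC window

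*SAP*

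**What the plan says.** **Rule that gives failure.** SAP 12.5.2, in the row for primary and secondary efficacy: "Participants who withdraw from the study prior to TOC will be considered not achieving success for the microbiological response". The next sentence imputes failure for these participants. SAP 7.2.6.1 says the same for the rectal and pharyngeal endpoints: "Participants who withdraw from the study prior to TOC will be considered not achieving success for the microbiological response and will be imputed as failures". Neither passage mentions the case where a culture is available.

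**Rule that gives success.** SAP 5.6: "Analysis visit labels will be assigned to each post-baseline record (including records from unscheduled and early termination visits) based on the corresponding study day". The TOC analysis window is Day 4 to 10 with target Day 6. Where several records fall in the window, "the record occurring closest to the target day will be utilized in all analyses and analysis population determinations". SAP 12.5.1 applies this to withdrawals: "All available data from participants who were withdrawn from the study will be listed and data will be included in summary tables" and figures, with a pointer to Section 5.6. Under SAP Table 2, a negative TOC culture without other systemic antimicrobials is a success.

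**The cultures are planned.** The TOC footnote to protocol Table 2 (specimen collection) reads: "Any participant that withdraws before TOC should have all bacteriology and NAAT assay collections performed as indicated at the TOC Visit". Protocol 8.2 adds: "Participants who withdraw from the study should be encouraged to return for the TOC and/or Follow-up Visits".

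No passage states which rule takes precedence.

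**The concern.** The primary response is assigned by a programmed algorithm, so each participant needs exactly one score. For one type of participant, the score depends on which SAP section the programmer follows. Read literally, the withdrawal sentence does more than fill in missing data: it replaces an observed, in-window negative culture with a failure.

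The literal reading also departs from the protocol. Protocol Table 5 and Section 10.4.2 count undetermined outcomes, other antimicrobial use and non-return for TOC as failures, but not withdrawal as such. SAP 2.1 reports no change to the protocol's planned analyses. The estimand does not settle the matter, because its two intercurrent events are treatment discontinuation and use of other antimicrobials, not study withdrawal.

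The question carries over to other analyses. In the Microbiologically Evaluable Population, such a participant can satisfy the criterion of an available TOC culture and still be scored a failure. The optional multiple-imputation and tipping-point runs on all missing responses (SAP 7.1.6.2) need to know whether this response is observed or missing. None of the sensitivity analyses listed there tests the choice.

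**Working it through.** **Step 1. Which withdrawers are affected?** The two rules side by side, for a participant who withdraws before TOC:

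| Situation | SAP 5.6 with SAP Table 2 | SAP 12.5.2 read literally | Conflict |
|---|---|---|---|
| No culture | Failure | Failure | No |
| Culture only before Day 4 or after Day 10 | No TOC label, failure | Failure | No |
| In-window culture, NG-positive | Failure | Failure | No |
| In-window culture, negative but out of stability | Unable to determine, failure | Failure | No |
| In-window culture, negative, other systemic antimicrobials before TOC | Failure | Failure | No |
| In-window culture, negative, in stability, no other systemic antimicrobials | **Success** | **Failure** | **Yes** |

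The clearest route to the last row is a participant who withdraws on Day 3 and returns on Day 6, as protocol 8.2 encourages. A second route is a participant booked for Day 7 who withdraws on Day 5 with a negative culture at the Early Withdrawal visit.

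**Step 2. The plan's own figure.** Inputs from protocol 10.2.1: 200 per arm, 90% success in both arms, margin 10 points, one-sided 0.025.

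Power = Phi(0.10 / sqrt(2 x 0.90 x 0.10 / 200) - 1.96) = Phi(0.10 / 0.03 - 1.96) = Phi(1.373) = 91.5%. The protocol states approximately 91%, so its figure is reproduced.

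**Step 3. What rescoring does to the noninferiority limit.** One participant in 200 is 1/200 = 0.5 percentage points. The lower limit is the value d below the observed difference that solves

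(p1 - p2 - d) / sqrt{ [q1(1 - q1)/n1 + q2(1 - q2)/n2] x N/(N - 1) } = 1.96,

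where p1 and p2 are the observed gepotidacin and comparator rates, q1 and q2 are the maximum-likelihood rates constrained to q1 - q2 = d, n1 = n2 = 200 and N = 400. This is the unstratified Miettinen-Nurminen limit. The primary analysis is stratified by sex and sexual orientation, so these values are indicative.

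The documents give no count of affected participants, so the number rescored from success to failure is an assumption, shown over a range:

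| Rescored | Gepotidacin | Comparator | Lower limit |
|---|---|---|---|
| None | 180/200 | 180/200 | -6.05% |
| 2 gepotidacin | 178/200 | 180/200 | -7.19% |
| 5 gepotidacin | 175/200 | 180/200 | -8.88% |
| 7 gepotidacin | 173/200 | 180/200 | -9.99% |
| 8 gepotidacin | 172/200 | 180/200 | -10.55% |
| 2 comparator | 180/200 | 178/200 | -5.15% |
| 5 comparator | 180/200 | 175/200 | -3.80% |
| 2 in each arm | 178/200 | 178/200 | -6.29% |
| 5 in each arm | 175/200 | 175/200 | -6.61% |

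Imputing failure is therefore not conservative in every case. If the affected participants are mainly in the comparator arm, it moves the limit towards noninferiority.

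**The case against.** The strongest reply is that the withdrawal sentence is only a missing-data rule. It stands under a missing-data heading and speaks of imputation, and an in-window culture is not missing. In 7.2.6.1 it directly follows a sentence about participants who do not return or lack TOC data. Section 12.5.1, just before it, sends withdrawn participants' data to 5.6, and the outcome algorithm in SAP Table 2 does not mention withdrawal. The narrow reading, covering only withdrawers without a TOC-window culture, may well be what the authors meant.

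This makes the intent plausible but does not put it in the text. On the narrow reading the sentence adds nothing to the neighbouring bullet that fails undeterminable outcomes. That is weak evidence either way, because the first bullet, on non-return, overlaps with it too. The literal words still cover a participant who withdraws on Day 3 and returns on Day 6. The Day 5 example is less clear-cut: once its culture carries the TOC label, one can argue that the participant did not withdraw before TOC in analysis terms.

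A reader might also infer that withdrawal will differ between arms, given open-label treatment and different tolerability. The documents do not establish this. Under protocol 8.1, participants who stop treatment for an adverse event are not considered withdrawn and should attend TOC, and adverse events are not among the withdrawal reasons in protocol 8.2. A difference remains possible, since consent withdrawal and investigator discretion are listed and adverse events leading to study withdrawal are tabulated.

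**Conclusion.** The conflict is real but narrow. SAP 12.5.2 and 7.2.6.1 as written impute failure for every participant who withdraws before TOC. SAP 5.6, SAP 12.5.1 and SAP Table 2 would score some of the same participants as successes. Only withdrawers with a Day 4 to 10, in-stability, NG-negative culture and no other systemic antimicrobials are affected. The number is not given and is probably small, since participants lost to follow-up will usually have no culture.

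Two stronger readings should be resisted. A reader might infer that any culture from a withdrawn participant is scored two ways; the first table shows that every other case is failure under both rules. A reader might also infer that a single participant could decide noninferiority. That is true only at the chosen edge between 173 and 172 gepotidacin successes against 180. From equal arms of 180/200, eight reclassifications confined to gepotidacin are needed to lose noninferiority. Nothing in the documents supports any particular rate of such cases in one arm.

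These sizes rest on 200 per arm, 90% success in both arms and unstratified limits. The conflict between the texts does not depend on them. It should be settled before unblinding, because a later choice would be a post hoc decision on the primary endpoint.

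**What to change.** In SAP 12.5.2 and 7.2.6.1, replace the withdrawal sentence with wording such as:

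> *Participants who withdraw and have no evaluable culture in the TOC analysis window are imputed as failures. Any culture obtained within that window, whether at a TOC, unscheduled or Early Withdrawal visit, is scored by Table 2 regardless of withdrawal status.*

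The rule on other systemic antimicrobials stays as it is. This brings the SAP into line with protocol Table 5 and with SAP 5.6 and 12.5.1. It also makes clear that such a response is observed, not missing, for the Microbiologically Evaluable Population and the imputation analyses.

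The cost is SAP wording in two places before unblinding, with no new data.
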